7.1. Discontinuation of Study Intervention

In rare instances, it may be necessary for a participant to permanently discontinue (definitive discontinuation) study intervention. If study intervention is definitively discontinued, the participant will remain in the study to be evaluated for all planned efficacy and safety measurements. See the SoA (Section 1.3) for data to be collected at the time of discontinuation of study intervention and follow-up and for any further evaluations that need to be completed.

Possible reasons leading to permanent discontinuation of study intervention include:

Participant Decision

The participant requests to discontinue study intervention.

Discontinuation due to a hepatic event or liver test abnormality.

Participants who are discontinued from study intervention due to a hepatic event or liver test abnormality should have additional hepatic safety data collected via the eCRF (Section 10.5, Appendix 5). Discontinuation of the study intervention for abnormal liver tests **should be** considered by the investigator when a participant meets 1 of the following conditions after consultation with the Lilly's CRP or CRS:

- ALT or aspartate aminotransferase (AST) >8X upper limit of normal (ULN)
- ALT or AST >5X ULN for more than 2 weeks
- ALT or AST >3X ULN and total bilirubin level (TBL) >2X ULN or international normalized ratio (INR) >1.5
- ALT or AST >3X ULN with the appearance of fatigue, nausea, vomiting, right upper-quadrant pain or tenderness, fever, rash, and/or eosinophilia (>5%)
- Alkaline phosphatase (ALP) >3X ULN
- ALP >2.5X ULN and TBL >2X ULN
- ALP >2.5X ULN with the appearance of fatigue, nausea, vomiting, right quadrant pain or tenderness, fever, rash, and/or eosinophilia (>5%)

Additional circumstances in which participants will be discontinued from the study intervention include:

A participant will be discontinued from study intervention due to any of the following:

- If a participant is inadvertently enrolled and it is determined that continued study intervention would not be medically appropriate (See Section 7.2.1)
- If a participant misses 3 continuous injections
- Acute or chronic pancreatitis

- If a participant is diagnosed with an active or untreated malignancy (other than basal or squamous cell skin cancer, in situ carcinomas of the cervix, or in situ prostate cancer) after randomization
- If a participant is diagnosed with C-cell hyperplasia or medullary thyroid carcinoma (MTC) after randomization

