- Any other treatment-emergent AE (TEAE), SAE, or clinically significant laboratory value for which the investigator believes that permanent study intervention discontinuation is the appropriate measure to be taken
- Any significant study intervention-related hypersensitivity reaction;
- If any other antihyperglycemic medications except for study-specified concomitant OAMs and insulin is initiated, and the participant refuses to discontinue these medications
- If female participant becomes pregnant (Section 7.2)
- If a participant is diagnosed with T1D
- If an investigator, site personnel performing assessments, or participant is unblinded
- if the participant or the participant's designee, for example, legal guardian, requests that the participant be withdrawn from study intervention
- If the investigator or sponsor decides that the participant should be withdrawn from study intervention; if the investigator decides to permanently discontinue study intervention because of an SAE or a clinically significant laboratory value, Lilly or its designee should be alerted immediately.

Participants who discontinue the study intervention permanently will receive another glucose-lowering intervention (Section 6.5) and will continue participating in the study according to the protocol to collect all planned efficacy and safety measurements.

See the SoA for data to be collected at the time of intervention discontinuation and follow-up and for any further evaluations that need to be completed.

7.1.1. **Temporary Discontinuation**

In certain situations, after randomization, the investigator may need to temporarily discontinue (interrupt) study intervention (for example, due to an AE or a clinically significant laboratory value). If study intervention interruption is due to an AE, the event is to be documented and followed according to the procedures in Section 10.3 of this protocol. Every effort should be made by the investigator to maintain participants on study intervention and to restart study intervention after any temporary interruption, as soon as it is safe to do so.

Investigators should inform the Sponsor that study intervention has been temporarily interrupted. The data related to temporary interruption of study intervention will be documented in source documents and entered in the eCRF.

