All hypersensitivity reactions will be reported by the investigator as either AEs or, if any serious criterion is met, as SAEs. Additional data, such as type of reaction and treatment received, will be collected on the hypersensitivity reaction eCRF for any AEs or SAEs deemed related to study intervention by the investigator. In the event of severe hypersensitivity reactions (i.e., generalized urticaria or anaphylaxis), serum and plasma samples should also be collected as close as possible to the occurrence of the event. Samples for follow-up assessment may also be collected within 4 weeks of the recovery from the event. Study intervention should be temporarily interrupted in any individual suspected of having a severe or serious allergic reaction to study intervention (Section 7.1.1). Study intervention may be restarted when/if it is safe to do so, in the opinion of the investigator. It is recommended that participants who experience a systemic hypersensitivity reaction be treated per the local standard of care.

If study intervention is permanently discontinued, the participant will receive another glucose-lowering treatment, judged by the investigator to be appropriate based on the participant's clinical status, and will continue in the study to collect all planned efficacy and safety measurements.

Injection site reactions will be collected on an eCRF separate from the hypersensitivity reaction eCRF.

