9.3. Populations for Analyses

The following analysis populations are defined in [Table 1](#).

Table 1. Populations for Analyses

Population	Description
Entered	All participants who sign the ICF.
Randomized	All participants who are randomized to a treatment arm.
Nonrandomized	All participants entered, but not randomized to a treatment arm.
Intention-to-treat (ITT) set	All randomly assigned participants who are exposed to at least 1 dose of study intervention for an assigned treatment arm. Participants will be included in the treatment group they were randomized to.
Efficacy analysis set for Period I (EAS1)	Data obtained during Treatment Period I (26-week) from the ITT set, excluding data after initiating rescue antihyperglycemic medication or discontinuing study intervention (last dose date + 7 days). In the event of a treatment error, participants will be

	analyzed according to the treatment they were randomly assigned to receive.
Safety analysis set for Period I (SS1)	Data obtained during Treatment Period I from the ITT set, regardless of adherence to study intervention or initiation of rescue antihyperglycemic medication.
Efficacy analysis set for Period I and II (EAS2)	Data obtained during Treatment Period I and II (52-week) from the ITT set, excluding data after initiating rescue antihyperglycemic medication or discontinuing study intervention (last dose date + 7 days). In the event of a treatment error, participants will be analyzed according to the treatment they were randomly assigned to receive.
Safety analysis set for Period I and II (SS2)	Data obtained during both Treatment Period I, II and safety F/U period from the ITT set, regardless of adherence to study intervention or initiation of rescue antihyperglycemic medication.

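### For a severe hypersensitivity reaction judged related to study drug, Protocol 7.1 requires a permanent stop while 8.3.3 with 7.1.1 leaves restart open, and nothing says which governs

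*Protocol*

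**What the plan says.** Protocol 7.1, on permanent discontinuation, introduces a mandatory list: "A participant will be discontinued from study intervention due to any of the following". One entry is "Any significant study intervention-related hypersensitivity reaction". The protocol does not define *significant*, and the entry does not refer to the hypersensitivity text elsewhere.

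Protocol 8.3.3, under Hypersensitivity Reactions, sets a different action: "Study intervention should be temporarily interrupted in any individual suspected of having a severe or serious allergic reaction to study intervention". It cites Section 7.1.1 and continues: "Study intervention may be restarted when/if it is safe to do so, in the opinion of the investigator". Shortly before, in a sentence about blood sampling, the same subsection explains severe reactions as generalized urticaria or anaphylaxis. Its next paragraph begins "If study intervention is permanently discontinued, the participant will receive another glucose-lowering treatment", and says the participant stays in the study for all planned measurements.

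Protocol 7.1.1, on temporary interruption in general, says "Every effort should be made by the investigator to maintain participants on study intervention and to restart study intervention after any temporary interruption". It makes the timing of restart conditional on safety.

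For the analysis, Protocol 9.3 and SAP Section 3 define EAS1 and EAS2 without the data that follow rescue medication or discontinuation of study drug, with the cut at last dose plus 7 days. Neither document states an exclusion for a temporary interruption. SAP 1.1.1.1 refers to Protocol Section 7 for the events that lead to treatment discontinuation.

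**The concern.** A severe allergic reaction attributed to study drug is hard to describe as not significant. An investigator who starts from 7.1 would stop such a participant for good. One who starts from 8.3.3 and follows its reference to 7.1.1 would interrupt and may then restart. Each would be following the protocol as written.

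What is at stake is first participant safety: someone whom 7.1 requires to stop could be re-exposed under 8.3.3. Second is consistency. Stopping study drug because of an adverse event is a secondary safety endpoint (Protocol Section 3, SAP 1.1), so which section a site follows decides whether the participant is counted. The same decision sets whether an intercurrent event has occurred for the efficacy estimand.

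**Working it through.** The plan gives no figure to reproduce. The check is a comparison of the texts.

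| | Protocol 7.1 | Protocol 8.3.3 with 7.1.1 |
|---|---|---|
| Trigger | Reaction that is significant and related to study drug | Suspicion of a severe or serious allergic reaction to study drug |
| Key term | *Significant*: not defined | *Severe*: explained by two examples in the sampling sentence |
| Action | Permanent stop, mandatory | Interruption advised; restart permitted (8.3.3) and encouraged once safe (7.1.1) |
| Test for restart | None | Safety, in the investigator's opinion; relatedness is not mentioned |
| Link to the other text | None to 8.3.3 | To 7.1.1 only, not to the 7.1 list |

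**Step 1: do the triggers overlap?** Yes. Anaphylaxis judged related to study drug meets 8.3.3 by its own example. It also meets 7.1 on any ordinary meaning of *significant*.

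**Step 2: do the actions agree there?** No. Section 7.1 leaves no route back to treatment. Section 8.3.3 leaves one open, and 7.1.1 encourages it.

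**Step 3: does any text set precedence?** None was found. Section 8.3.3 uses relatedness to decide whether the hypersensitivity eCRF is completed, but does not use it to limit restart.

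**Step 4: how does the protocol handle a comparable case?** For acute pancreatitis, the same Section 8.3.3 separates work-up on suspicion from action on diagnosis, and requires study drug to be stopped on diagnosis. That matches the pancreatitis entry in the 7.1 list. No such link is written for hypersensitivity.

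**Step 5: what follows in the data for one participant?** Assume, for illustration only, that the last dose before the reaction is at Week 8. HbA1c is scheduled after baseline at Weeks 8, 16, 26, 38 and 52.

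- Permanent stop: the cut falls at Week 8 + 7 days = Week 9. Weeks 16 and 26 leave EAS1 (2 of 3 post-baseline values). Weeks 16, 26, 38 and 52 leave EAS2 (4 of 5). The participant adds 1 to the count of discontinuations for adverse events.
- Restart after one or two missed weekly doses: no value is excluded on this ground, and the participant adds 0 to that count. A third consecutive missed injection would itself trigger discontinuation under 7.1.

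The number of such participants cannot be derived from the documents, so this cannot be scaled to the trial.

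**The case against.** The strongest reply is that the sections describe two stages: interrupt on suspicion, stop permanently if the reaction proves significant and related, and otherwise restart if safe. The wording lends this support. Section 8.3.3 speaks of suspected cases and 7.1 of related ones. Restart is permissive and conditional on safety, a limit that 7.1.1 shares. Section 8.3.3 itself foresees permanent discontinuation. An investigator who interrupts and does not restart complies with both.

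There are also safeguards. Section 8 asks for immediate safety concerns to be discussed with the sponsor. Section 7.1.1 asks for the sponsor to be told of interruptions. Section 8.3.1 requires serious events to be reported within 24 hours. Section 7.1 ends treatment after three consecutive missed injections.

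Much of this stands. A reader might infer that the sections give opposite instructions; they do not, because the triggers differ and a staged reading is possible. A reader might also infer that a permanent stop loses all later efficacy data. It does not: the participant remains in the study and is measured, earlier values still enter the MMRM, and later safety data stay in SS1 and SS2.

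What the reply does not settle is the overlap. The staged reading is plausible but unwritten, and the restart sentence does not depend on relatedness. The safeguards make sponsor contact likely, but they do not tell the sponsor or the site which section applies.

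**Conclusion.** The point holds as an unresolved overlap. For a severe reaction judged related to study drug, 7.1 and 8.3.3 with 7.1.1 do not agree, and following 8.3.3 as written can re-expose a participant whom 7.1 requires to stop.

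This rests on one reading: that a severe, related reaction is *significant* in the sense of 7.1. The absence of a definition is part of the defect.

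The size is small in numbers and potentially serious for the individual. That cases will be few is an assumption, since the documents give no rate. For the same reason no effect on power or on the HbA1c estimate can be shown, and a reader should not infer a threat to the primary result. The effects on the discontinuation endpoint and the efficacy sets are real for each affected participant but secondary. The correction is worth making for safety and uniform conduct.

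**What to change.** Reconcile Protocol 7.1, 7.1.1 and 8.3.3:

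- Use one set of defined terms (significant, severe, serious, suspected, related) in all three places.
- Refer to the 7.1 discontinuation list in the 8.3.3 sentence on restart.
- State which section governs once a reaction has been judged related to study drug.

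Which reactions lead to a stop and which allow restart is the sponsor's clinical decision; no view is offered here.

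No new coding rule is needed for EAS1 or EAS2. The cut at last dose plus 7 days is already stated and follows from what happened to study drug.

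The cost is a protocol wording change, with the ethics approval that Appendix 1 requires for amendments, and a clarification letter to sites. No change to the design, sample size or analysis programs is needed.

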8.4. Treatment of Overdose

For this study, if the duration of injections between 2 doses are within 72 hours of each other it will be considered an overdose.

In the event of an overdose, the investigator should:

1. Contact the clinical research associate (CRA) immediately.
2. Closely monitor the participant for any AE/SAE and laboratory abnormalities.

Decisions regarding dose interruptions or modifications will be made by the investigator in consultation with the CRP or CRS based on the clinical evaluation of the participant.

Effects of overdose with dulaglutide in clinical studies have included gastrointestinal disorders and hypoglycemia. In the event of overdose, appropriate supportive treatment should be initiated according to the participant's clinical signs and symptoms (IB).

8.5. Pharmacokinetics

Not applicable.

8.6. Pharmacodynamics

Not applicable.

8.7. Genetics

Not applicable.

8.8. Biomarkers

Not applicable.

8.9. Immunogenicity Assessments

There are no planned assessments for anti-dulaglutide antibodies for this study. However, plasma and serum samples may be used to evaluate antibody production to dulaglutide and dulaglutide drug concentrations, in the event of hypersensitivity reactions.

Samples may be stored for a maximum of 7 years (or according to local regulations) following the last participant's last visit for the study at a facility selected by the sponsor to enable further analysis of immune responses to dulaglutide.

8.10. Health Economics OR Medical Resource Utilization and Health Economics

Not applicable.

9. Statistical Considerations

9.1. Statistical Hypotheses

The alternative hypothesis for the primary objective is:

Dulaglutide 1.5 mg is superior to dulaglutide 0.75 mg, relative to the mean change in HbA1c from baseline at Week 26.

9.2. Sample Size Determination

Approximately 732 participants will be screened to achieve 585 participants randomly assigned in a 2:1 ratio to dulaglutide 1.5 mg group and dulaglutide 0.75 mg group (390 and 195 participants, respectively). Assuming a drop-out rate of 10%, 528 participants will be evaluable for an estimated total of 352 evaluable participants in the dulaglutide 1.5 mg group and 176 evaluable participants in the dulaglutide 0.75 mg group.

This sample size provides at least 90% power for demonstrating superiority of dulaglutide 1.5 mg to dulaglutide 0.75 mg in the HbA1c change from baseline at Week 26. This assumes a true treatment difference of -0.3% with a common standard deviation (SD) of 1.0% for the change in HbA1c from baseline.

For participants taking DPP-4i prior to randomization, target numbers of participants randomized for 1.5 mg and 0.75 mg are 150 and 75 (total 225 participants).

For participants taking other OAMs, target numbers of participants randomized for 1.5 mg and 0.75 mg are 240 (40 per OAM class) and 120 (20 per OAM class). In total, 360 participants (60 per OAM class) will be randomized for other OAMs.

9.3. Populations for Analyses

The following analysis populations are defined in [Table 1](#).

Table 1. Populations for Analyses

Population	Description
Entered	All participants who sign the ICF.
Randomized	All participants who are randomized to a treatment arm.
Nonrandomized	All participants entered, but not randomized to a treatment arm.
Intention-to-treat (ITT) set	All randomly assigned participants who are exposed to at least 1 dose of study intervention for an assigned treatment arm. Participants will be included in the treatment group they were randomized to.
Efficacy analysis set for Period I (EAS1)	Data obtained during Treatment Period I (26-week) from the ITT set, excluding data after initiating rescue antihyperglycemic medication or discontinuing study intervention (last dose date + 7 days). In the event of a treatment error, participants will be

	analyzed according to the treatment they were randomly assigned to receive.
Safety analysis set for Period I (SS1)	Data obtained during Treatment Period I from the ITT set, regardless of adherence to study intervention or initiation of rescue antihyperglycemic medication.
Efficacy analysis set for Period I and II (EAS2)	Data obtained during Treatment Period I and II (52-week) from the ITT set, excluding data after initiating rescue antihyperglycemic medication or discontinuing study intervention (last dose date + 7 days). In the event of a treatment error, participants will be analyzed according to the treatment they were randomly assigned to receive.
Safety analysis set for Period I and II (SS2)	Data obtained during both Treatment Period I, II and safety F/U period from the ITT set, regardless of adherence to study intervention or initiation of rescue antihyperglycemic medication.

9.4. Statistical Analyses

9.4.1. General Considerations

Statistical analysis of this study will be the responsibility of Lilly or its designee.

All tests of treatment effects will be conducted at a 2-sided alpha level of 0.05, unless otherwise stated, and all confidence intervals (CIs) will be given at a 2-sided 95% level.

Any change to the data analysis methods described in the protocol will require an amendment only if it changes a principal feature of the protocol. Any other change to the data analysis methods described in the protocol, and the justification for making the change, will be described in the SAP and the clinical study report. Additional exploratory analyses of the data will be conducted as deemed appropriate.

The primary efficacy assessment, guided by efficacy “estimand”, will be conducted using the EAS1/EAS2 to compare dulaglutide 1.5 mg with dulaglutide 0.75 mg. The “efficacy” estimand measures the benefit of treatment when taken as directed.

Unless specified otherwise, safety assessments will be guided by an estimand comparing safety of dulaglutide 1.5 mg with dulaglutide 0.75 mg, irrespective of adherence to study intervention or initiation of antihyperglycemic rescue therapy. Thus, the safety analyses will be conducted using the SS1 or SS2. Selected safety analysis (for example, hypoglycemia) may be conducted excluding data after initiation of another antihyperglycemic therapy.

Summary statistics for continuous measures will include sample size, mean, SD, median, minimum, and maximum. The analysis model to make comparisons among treatment arms relative to continuous measurements assessed over time will be a mixed-model for repeated measures (MMRM), with terms of treatment, visit and treatment by visit interaction, pre-study

OAM class (see stratification factors in Section 4.1), and baseline measurement as a covariate. An unstructured covariance matrix will model the relationship of within participant errors.

The Kaplan-Meier method will be used for estimation of cumulative event free survival rates over time, and Cox proportional hazards regression analysis will be used to compare hazard rates among treatments.

Summary statistics for categorical measures, including categorized continuous measures, will include sample size, frequency, and percentages. Fisher's exact test will be used to examine the treatment difference in categorical outcomes. Logistic regression may be used to examine the treatment difference in binary efficacy outcomes. Summary statistics for discrete count measures will include sample size, mean, SD, median, minimum, and maximum. The negative binomial regression model will be used for the treatment comparison of discrete count measures.

The statistical analysis plan (SAP) will be finalized prior to the first unblinding (for the 26 weeks primary outcome database lock) and it will include a more technical and detailed description of the statistical analyses described in this section. This section is a summary of the planned statistical analyses of the most important endpoints including primary and secondary endpoints.

